16.2.4. SENSITIVITY ANALYSES FOR SECONDARY EFFICACY ENDPOINTS

No sensitivity analyses will be performed for this sub-protocol.

16.2.5. SUPPLEMENTARY ANALYSES FOR SECONDARY EFFICACY ENDPOINTS

The only supplementary analyses that will be performed for this sub-protocol is that Kaplan-Meier product-limit estimates of the time to all-cause mortality through Day 29 as described in the Master SAP Section 16.2.5, but the hazard ratio of the Lanadelumab-IV + SoC vs. shared placebo + SoC, its associated two-sided 95% CI, and p-value based on the Cox proportional hazard model described in the Master SAP will not be provided.

16.3. EXPLORATORY EFFICACY

CCI [Redacted]
[Redacted]

16.4. ADDITIONAL EFFICACY

CCI [Redacted]
[Redacted]

16.5. INTERIM ANALYSIS

No IAs will be performed for this sub-protocol since enrollment into this sub-protocol was early terminated by the Sponsor before the trigger for the first IA was reached (refer to Master SAP Section 16.5).

17. SAFETY ENDPOINTS

[figure not shown]
The safety analyses will be performed as described in the Master COV-01 SAP based on the safety analysis set.

In addition, the following analyses will also be performed for the sub-protocol COV-01-001 based on the safety analysis set.

CCI [Redacted]

PPD [Redacted] Version Number: Amendment 3, v1.0
Version Date: 23-Jul-2021

CCI [Redacted]
[Redacted]
[Redacted]
[Redacted]

17.1. ADVERSE EVENTS

17.1.1. ADVERSE EVENTS OF SPECIAL INTEREST

The following are defined as adverse events of special interest (AESIs) for Lanadelumab-IV and will be identified based on investigator-reported AESIs on the AE page of the CRF:

- Hypersensitivity reactions (refer to [Appendix 1](#));
- Events of disordered coagulation (i.e., bleeding AESIs or hypercoagulable AESIs; refer to [Appendix 2](#))

A summary of AESIs, overall and by AESI category and PT will be prepared by treatment arm for patients randomized to COV-01-001 only. Should a patient experience multiple events within an AESI category or PT, the patient will be counted only once for that AESI category or PT. Additionally, the risk difference of the overall incidence rates of having any treatment-emergent AESI between the treatment arms will be presented along with its 95% two-sided Wald CI.

A listing of all AESIs will be provided.

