17.1. ADVERSE EVENTS

Each AE will be classified as either:

- Prior, defined as any AE that started or worsened in severity on or after the date of signed informed consent but before the first dose of study drug;
- Treatment-emergent, defined as any AE that started or worsened in severity on or after the first dose of study drug.

If time of the first dose of study drug and time of start of AEs are available, then the times will be taken into account for determining TEAEs. Refer to [Appendix 1](#) for handling of partial and completely missing dates for AEs. In the case where it is not possible to define an AE as treatment emergent or not, the AE will be classified by the worst case; i.e. treatment emergent.

AEs will be coded using the MedDRA dictionary, version 23.1 or later. Summaries by System Organ Class and PT will be sorted as follows: System Organ Classes will be sorted in alphabetical order and within each System Organ Class, PTs will be sorted by decreasing order to total frequency.

An overall summary of number and percentage of patients within each of the categories described in the sub-sections below will be provided by treatment arm. Should a patient experience multiple events within a category, the patient will be counted only once for that category. Additionally, the risk difference of the overall incidence rates of serious TEAEs and overall incidence rates of AESIs (when applicable for a sub-protocol) between treatment and control arms will be presented along with its 95% two-sided Wald CI.

[figure not shown]
All AEs (prior and TEAE) will be listed.

CCI

PPD

Version Number: Amendment 1, v1.0
Version Date: 23Apr2021

CCI

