4.5.2. FINAL ANALYSIS

For final analysis of this sub-protocol, the control arm (also referred to as shared placebo + SoC arm) will include all patients randomized to the placebo arm of any sub-protocol before this sub-protocol was early terminated (refer to section 3.3) at a site at which:

- This sub-protocol was opened for enrollment.
- At least one patient was randomized to either this sub-protocol active (Lanadelumab- intra-venous [IV] + SoC) or placebo (placebo to Lanadelumab-IV + SoC) arms.

That is, patients that satisfy these criteria will be included in the control arm of this sub-protocol regardless of 1) whether patients was randomized before this sub-protocol was opened for enrollment at the site (that is, patients randomized after enrollment into COV-01-001 sub-protocol was early terminated will be excluded from the control

arm of this sub-protocol) and 2) patient’s eligibility to this sub-protocol specific inclusion/ exclusion criteria.

The purpose of this change from the Master SAP control arm definition (Master SAP Section 4.5) is to minimize the randomization imbalance issue noted by the CCI Unblinded Biostatistician and IDMC members at the time of CCI. At the time this sub-protocol SAP was finalized, the randomization imbalance was estimated to be approximately 7:1 between this sub-protocol active and control arms, should the original control arm definition would have been retained for the final analysis of this sub-protocol.

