16. EFFICACY ENDPOINTS

Given that only 29 patients were randomized into COV-01-001 sub-protocol and that is expected ~34 patients will be included in final analysis of this sub-protocol when taking the shared placebo arm into account instead of ~700 as required by the sample size (refer to Master SAP Section 7.1), no statistical inferences will be performed for any efficacy endpoint, but two-sided 95% exact binomial Confidence Interval (CI) within each treatment arm will be provided, when possible.

In conformance with the FDA’s Guidance for Submission of Abbreviated Report and Synopsis in Support of Marking and publication requirements of *ClinicalTrials.gov*, summary tables will be presented for the primary and key secondary efficacy endpoints (refer to Master SAP Sections 16.1.1, 16.2.1.1, 16.2.1.2, and 16.2.1.3). Although not required by the previously mentioned FDA’s Guidance, summary tables will also be provided for the other secondary efficacy endpoints (refer to Master SAP Sections 16.2.1.4 to 16.2.1.9) in order to be compliant with the publication requirements of *ClinicalTrials.gov*.

Efficacy summaries will be performed as described in the Master COV-01 SAP, except that all endpoints will be analyzed on the primary analysis set (refer to Section 5.1) instead of the FAS.

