4.5.2. FINAL ANALYSIS

For final analysis of this sub-protocol, the control arm (also referred to as shared placebo plus standard of care (SoC) arm) will include all patients randomized to the placebo arm of any sub-protocol at a site at which:

- This sub-protocol was opened for enrollment.
- At least one patient was randomized to either this sub-protocol active (zilucoplan plus SoC) or placebo (placebo to zilucoplan plus SoC) arms.

That is, patients that satisfy these criteria will be included in the control arm of this sub-protocol regardless of 1) the timing of patient’s randomization into a sub-protocol (i.e., regardless of if patient was randomized before or after this sub-protocol was opened for enrollment at the site) and 2) patient’s eligibility to this sub-protocol specific inclusion/ exclusion criteria.

The purpose of this change from the Master SAP control arm definition (Master SAP Section 4.5) is to minimize the randomization imbalance issue noted by the CCI Unblinded Biostatistician and IDMC members at the time of CCI [Redacted] At the time this sub-protocol SAP was finalized, the randomization imbalance was estimated to be approximately 7:1

CCI [Redacted]	[Redacted]	Version Number:	Amendment 2, v1.0
PPD [Redacted]	[Redacted]	Version Date:	28-Jul-2021
CCI [Redacted]	[Redacted]		
[Redacted]	[Redacted]		

CCI [Redacted]

between this sub-protocol active and control arms, should the original control arm definition would have been retained for the final analysis of this sub-protocol.

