16. EFFICACY ENDPOINTS

Given that only 108 patients were randomized into COV-01-005 sub-protocol by the time enrollment into this sub-protocol was terminated early by the Sponsor and that is expected that less than the third of the total number of patients required by the sample size (i.e., ~700; refer to Master SAP Section 7.1) will be included in the final analysis of this sub-protocol, no statistical inferences will be performed for any efficacy endpoint, but two-sided 95% confidence interval (CI) within each treatment arm will be provided, when possible.

In conformance with the FDA's Guidance for Submission of Abbreviated Report and Synopsis in Support of Marking, summary tables will be presented for the primary and key secondary efficacy endpoints (refer to Master SAP Sections 16.1.1, 16.2.1.1, 16.2.1.2, and 16.2.1.3). Although not required by the previously mentioned FDA's Guidance, summary tables will also be provided for the other secondary efficacy endpoints (refer to Master SAP Sections 16.2.1.4 to 16.2.1.9) in order to be compliant with the publication requirements of *ClinicalTrials.gov*. In addition, summary tables will also be provided for the additional efficacy endpoint of incidence of all-cause mortality through Day 60 (refer to Master SAP Section 16.4.1.1).

[figure not shown]
Efficacy summaries will be performed as described in the Master COV-01 SAP.

CCI

PPD

Version Number: Amendment 2, v1.0
Version Date: 28-Jul-2021

CCI

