17.1. ADVERSE EVENTS

17.1.1. ADVERSE EVENTS OF SPECIAL INTEREST

The following are defined as adverse events of special interest (AESIs) for this sub-protocol and will be identified based on pre-defined coded preferred terms (PTs), high-level terms (HLTs, and/or system organ class:

- Anaphylactic reactions (Medical Dictionary for Regulatory Activities [MedDRA] algorithmic approached; refer to [Appendix 1](#));
- Serious anaphylactic reactions (MedDRA algorithmic approached; refer to [Appendix 1](#));
- Hypersensitivity reactions (standardized MedDRA query [SMQ] – narrow scope; refer to [Appendix 2](#));
- Serious hypersensitivity reactions (SMQ – narrow scope; refer to [Appendix 2](#));
- Infections (MedDRA system organ class of ‘Infections and infestations’);
- Serious infections (MedDRA system organ class of ‘Infections and infestations’);
- Neisseria infections (MedDRA high level term [HLT] of ‘Neisseria infections’);
- Serious Neisseria infections (HLT of ‘Neisseria infections’);
- Drug related hepatic disorders (SMQ – comprehensive search; refer to [Appendix 3](#)), excluding the ‘Liver neoplasms, benign (incl. cysts and polyps)’ and ‘Liver neoplasms, malignant and unspecified’ sub-SMQs.

A summary of treatment-emergent (refer to Master COV-01 SAP Section 17.1) AESIs overall and by AESI category and preferred term (PT) will be prepared by treatment arm for patients randomized to COV-01-005 only. Should a patient experience multiple events within an AESI category or PT, the patient will be counted only once for that AESI category or PT. The risk difference of the overall incidence rates of having any treatment-emergent AESI between the treatment arms will be presented along with its two-sided 95% Wald CI. A listing of all AESIs will be provided for patients randomized to COV-01-005 only.

CCI

PPD

Version Number: Amendment 2, v1.0
Version Date: 28-Jul-2021

CCI

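### The Wald 95% interval for the AESI risk difference in COV-01-001 and COV-01-005 is unreliable with roughly 4 and 13 own-placebo patients at most

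*SAP*

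**What the plan says.** Section 17.1.1 of the COV-01-001 SAP limits the AESI summary to patients randomized to that sub-protocol. In the same paragraph it says the risk difference for any treatment-emergent AESI "will be presented along with its 95% two-sided Wald CI". Section 17.1.1 of the COV-01-005 SAP has the same restriction, and its risk difference "will be presented along with its two-sided 95% Wald CI". Neither gives a rule for small arms or zero cells.

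The numbers are small:

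- COV-01-001 SAP, section 16: "Given that only 29 patients were randomized into COV-01-001 sub-protocol", and about "34 patients will be included in final analysis of this sub-protocol when taking the shared placebo arm into account".
- COV-01-001 SAP, section 4.5.2: under the Master SAP control definition, "the randomization imbalance was estimated to be approximately 7:1 between this sub-protocol active and control arms".
- COV-01-005 SAP, section 16: "Given that only 108 patients were randomized into COV-01-005 sub-protocol".
- COV-01-005 SAP, section 4.5.2: "the randomization imbalance was estimated to be approximately 7:1".

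Master SAP 17.1 sets the general rule, also with Wald limits, for "the risk difference of the overall incidence rates of serious TEAEs and overall incidence rates of AESIs". Master SAP 17 rules out statistical comparison of the arms on safety data, so the interval is descriptive.

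**The concern.** The Wald interval estimates each arm's variance from its observed proportion. If placebo has no events, its variance term is exactly zero, so the interval treats the placebo risk as known to be 0% on the strength of about 4 or 13 patients. It can then lie wholly above zero and read as a harm signal that the data cannot support. If neither arm has an event, it has zero width. When placebo does have events, Wald is not always too narrow, but it is badly placed.

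The interval would be printed, labelled 95%, beside the risks singled out for each agent. Both SAPs already use exact binomial intervals for efficacy percentages. In COV-01-001 the modification history shows the Wald interval added in Amendment 1 (27 April 2021), before enrollment stopped on 3 May 2021. Amendment 2 then added exact intervals for efficacy and left the safety interval as it was.

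**Working it through.** **Own-placebo counts.** The SAPs give no arm counts, so these are bounds. The control group defined in Master SAP 4.5 already contains the sub-protocol's own placebo patients, so own placebo P is at most control C, and C is about A/7, where A is the active arm. With A + P = N, P is at most N/8.

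- COV-01-001: 29/8 = 3.6, taken as 25 versus 4 (26 versus 3 as a check).
- COV-01-005: 108/8 = 13.5, taken as 95 versus 13 (94 versus 14 gives similar results).

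These are randomized counts; safety-set counts are not stated.

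**Interval.** Wald: p1 - p2 ± 1.96 × √[p1(1 - p1)/n1 + p2(1 - p2)/n2].

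For 4/25 versus 0/4: 0.16 ± 1.96 × √(0.16 × 0.84/25 + 0) = 0.16 ± 0.144, or 1.6% to 30.4%. The exact (Clopper-Pearson) upper limit for the placebo risk is 60% at 0/4 and 25% at 0/13, yet its variance term is 0.

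| Active vs placebo | Wald | Newcombe |
|---|---|---|
| 0/25 vs 0/4 | 0% to 0% | -49.0% to 13.3% |
| 3/25 vs 0/4 | -0.7% to 24.7% | -37.6% to 30.0% |
| 4/25 vs 0/4 | 1.6% to 30.4% | -33.9% to 34.7% |
| 4/95 vs 0/13 | 0.2% to 8.2% | -18.7% to 10.3% |
| 10/95 vs 0/13 | 4.4% to 16.7% | -12.8% to 18.3% |
| 5/25 vs 1/4 | -50.2% to 40.2% | -51.3% to 23.0% |

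Fisher's exact p is 1.0 for both 4-event examples. With no placebo events, Wald first excludes zero at 4 active events in either sub-protocol; Newcombe does so at 14/25 and 23/95. Miettinen-Nurminen limits are close to Newcombe (-35.5% to 35.0% for 4/25 versus 0/4). The last row shows Wald wider than Newcombe.

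**Coverage.** All pairs of binomial outcomes were enumerated. The true risks are assumed.

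| Equal true risk | 5% | 10% | 15% | 20% | 30% | 50% |
|---|---|---|---|---|---|---|
| Wald coverage, 25 vs 4 | 97% | 84% | 71% | 66% | 72% | 86% |
| Wald wholly above zero, 25 vs 4 | 3% | 16% | 28% | 31% | 23% | 7% |
| Wald coverage, 95 vs 13 | 64% | 74% | 87% | 91% | 91% | 92% |
| Wald wholly above zero, 95 vs 13 | 36% | 25% | 12% | 8% | 7% | 4% |

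The nominal value for lying wholly above zero is 2.5%. Newcombe coverage is about 94% to 96% in every column for both splits. At 26 versus 3, Wald coverage at 10/15/20/30% is 79/63/57/63%.

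With unequal risks at 25 versus 4, Wald coverage is 93% (active 15%, placebo 5%), about 84% (20%, 10%), 47% (5%, 15%) and 57% (10%, 20%).

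**Zero-width interval.** The chance of no events in either arm is (1 - risk)^N. For N = 29 it is 22.6% at a 5% risk and 4.7% at 10%. For N = 108 it is 0.4% at 5%.

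**Serious TEAEs.** Master SAP 17.1 uses the full control arm. In COV-01-001 that is about 34 - 25 = 9. At 25 versus 9, Wald coverage is 86% to 91% at equal risks of 10% to 50%. At the planned 350 per arm it is 94.6% to 95.4% at risks of 1% to 50%.

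**The case against.** **The interval is descriptive.** No decision rule uses it, both sub-protocols get abbreviated reports, and the counts and listings sit beside it. This stands, and it limits the weight of the point. It does not make a 0% to 0% interval, or one that excludes zero where Fisher's p is 1.0, a fair account of uncertainty.

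**Rates may fall where Wald does better.** COV-01-005 AESIs include the whole infections system organ class and a broad hepatic search, so the risk may be high. The chance of 0/13 placebo events is 5.5% at a 20% risk and 1.0% at 30%, and coverage there is 91% to 92%. The most striking COV-01-005 figures therefore depend on a low rate. For COV-01-001, sub-protocol section 4.1.1.2 calls AESI incidence low in hereditary angioedema patients. At 5% risk Wald coverage is 97%, and the remaining defect is the zero-width interval. No rate is given for hospitalized COVID-19 patients, and at 10% to 30% the failure in COV-01-001 is severe.

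**The risk difference might use the shared control.** The restriction to own patients is attached to the summary and, in COV-01-005, to the listing, but is not repeated in the risk-difference sentence; Master SAP 17.1 refers to the control arm. On that reading COV-01-001 has about 9 controls and still falls short. COV-01-005 has an unstated, larger number: at an illustrative 95 versus 40, coverage is 93% to 94% at risks of 10% or more, and the point largely fades. The single-paragraph wording makes own placebo the more natural reading.

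**Conclusion.** The Wald interval is the wrong choice for these two comparisons. The case is strongest in COV-01-001, where about 4 placebo patients bring coverage to 66% to 84% at equal risks of 10% to 30%. In COV-01-005 it is serious at risks of 5% to 10% (64% to 74%) and modest from 20% upward. This rests on placebo counts inferred from an approximate 7:1 ratio, on randomized rather than safety-set numbers, on assumed AESI rates, and on reading the comparison as own patients only. The harm is a misleading safety display; no formal error rate is affected. It should be corrected before the tables are produced.

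**What to change.** In section 17.1.1 of each of the two sub-protocol SAPs, replace the Wald interval with a Miettinen-Nurminen or Newcombe score interval, and say in that sentence which patients the risk difference uses. Apply the same method to the serious-TEAE risk difference from Master SAP 17.1 when it is produced for these two sub-protocols. The need there is clearest in COV-01-001. The Master SAP text can stay as it is for a comparison at 350 per arm.

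The cost is one option in the SAS call and one line in each of two SAPs, with no change to data, endpoints or conduct. Intervals will usually be wider when placebo has no events.

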17.2. LABORATORY EVALUATIONS

In addition to the laboratory tests listed in Appendix 5 of the Master COV-01 SAP, the fibrin degradation products (FDPs) will be included in the outputs.

The analysis for laboratory parameters is described in the Master COV-01 SAP.

17.3. VITAL SIGNS

Analysis of vital signs data will be performed as described in the Master COV-01 SAP.

17.4. ECG EVALUATION

Electrocardiogram (ECG) evaluation will be performed at screening and on the day of discharge from the hospital. The following ECG parameters will be collected:

CCI

PPD

Version Number: Amendment 3, v1.0
Version Date: 23-Jul-2021

CCI

- Heart rate (beats per minutes [bpm]);
- PR interval (milliseconds [msec]);
- RR interval (msec);
- QRS interval (msec);
- QT interval (msec);
- QTc interval (msec);
- QTcB interval (msec);
- QTcF interval (msec);
- Overall ECG interpretation as assessed by Investigator (normal; abnormal, not clinically significant; and abnormal, clinically significant).

The observed and change from baseline values of each continuous ECG parameter will be summarized using descriptive statistics by treatment arm and visit based on the safety analysis set.

Number and percentage of patients in each category of the overall ECG interpretation as assessed by the Investigator will also be provided by treatment arm and visit based on the safety analysis set.

17.5. PHYSICAL EXAMINATION

Analysis of physical examination data will be performed as described in the Master COV-01 SAP.

18. PHARMACOKINETICS

[figure not shown]
PK concentrations of Lanadelumab-IV will be summarized by visit and timepoint (refer to Section 3.2) based on the PK analysis set (refer to Section 5.2) overall and broken down further by the ordinal scale for clinical severity score at baseline (2 or 3 to 5). Concentrations that are below the limit of quantification (BLQ) will be treated as a numeric value of zero and will be excluded from the geometric statistics. All PK concentrations will be reported and analyzed with 3 significant figures. For the reporting of descriptive statistics, the mean, standard deviation, standard error (if reported), and confidence interval (if reported) will be presented to one digit more precision than the source

CCI

PPD

Version Number: Amendment 3, v1.0
Version Date: 23-Jul-2021

CCI

data. The minimum, median, and maximum will be presented to the same precision as the source data. Coefficient of variation will always be reported to 2 decimal places.

For Day 1, PK concentrations of Lanadelumab-IV will be summarized for the pre- and post-infusion separately.

Post-dose timepoints will be presented for Days 4, 7, 15, 29, and day of discharge as PK blood samples can be collected at any time during each of these days.

PK concentrations will be listed according to nominal time points scheduled.

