- h To be assessed only while hospitalized.
- i Includes oxygen requirement (ie, mode of delivery/liters of oxygen flow, FiO2 requirement), stop date of oxygen for patients who were discharged on home oxygen, extracorporeal membrane oxygenation support, noninvasive or invasive ventilator requirement, including start and stop of low- or high-flow oxygen supply or of any form of ventilation, and need for renal replacement therapy. Noninvasive ventilation refers to the delivery of mechanical ventilation to the lungs using techniques that do not require an endotracheal airway.
- j Only stop date of oxygen for patients who were discharged on home oxygen.
- k Information recorded is yes/no, hospitalization date, discharge date.
- l Laboratory tests performed within the 48 hours prior to enrolment will be accepted for determination of eligibility.
- m Hematology and clinical chemistry.
- n Hematology, clinical chemistry, liver function tests, cardiac panel, and coagulation.
- o Any laboratory tests performed as part of routine clinical care can be used for safety laboratory testing.
- p Hematology, clinical chemistry, and liver function tests.
- q If not done or entered into the eCRF within previous day.
- r Hematology, clinical chemistry, and liver function tests will be collected on the eCRF, if available, while the patient is in hospital.
- s This assessment will be performed on Day 15 or date of discharge, if earlier.

t *Samples for PK/PD assessments will be collected temporally as close as possible to Hour 0 (start of study drug infusion/dosing) within 60 minutes before the infusion as well as at the end of the infusion on Day 1 (within 30 minutes post infusion). If feasible, samples for PK and PD will be collected at Days 4, 7, 15, and 29 (or hospital discharge, if earlier) at any time during the day. Start and end of study drug infusion times (day, hour, minute) for each dose should be accurately recorded per 24-hour clock. All PK/PD sampling times (day, hour, minute) should be accurately recorded per 24-hour clock. No sample collection is required after discharge.* CCI

u *Antidrug antibody samples will be collected at Day 1 (pre-infusion within 30 minutes before the infusion) and at Days 15 and 29 (or hospital discharge, if earlier).*

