**Table 1 Predicted Clinical Exposure Margins Compared to Observed Exposure (NOAEL) in Cynomolgus Monkeys**

Cynomolgus Monkey Exposure (NOAEL)		GLP Toxicity Repeat-Dose IV Study (Day 21 to 28)	Non-GLP Tolerability Single-Dose IV Study (Day 0 to 28)
AUC last (µg*hr/mL)		123000	137500
C max (µg*mL)		1640	1155
Human 300 mga		Safety Margin	
AUC 0-672 (µg*hr/mL)	17281	7.1	8.0
C max (µg*mL)	94.1	17	12
Human 2×300 mgb		Safety Margin	
AUC 0-672 (µg*hr/mL)	33532	3.7	4.1
C max (µg*mL)	130	13	8.9

AUC0-672=area under the plasma concentration-time curve from time 0 to 672; AUClast=area under the plasma concentration-time curve from time 0 to the time of last concentration measured; Cmax=maximum plasma concentration; GLP=Good Laboratory Practice; IV=intravenous(y); NOAEL=No Observed Adverse Effect Level.

a Infused over 60 minutes on Day 1.

b Infused over 60 minutes on Days 1 and 4 (individual doses separated by 3 days).

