#### **4.2 Pharmacokinetic Assessments**

Plasma samples for PK analysis will be collected temporally as close as possible to Hour 0 (start of study drug infusion/dosing) within 60 minutes before the infusion as well as at the end of the infusion on Day 1 (within 30 minutes post infusion). If feasible, plasma samples for PK analysis will also be collected on Days 4, 7, 15, and 29 (or hospital discharge, if earlier) at any time during the day (Section 1.2). All PK sampling times (day, hour, minute) should be accurately recorded per 24-hour clock. No sample collection is required after discharge. PK samples are to be shipped to the study central laboratory and routed to a specialty laboratory for analysis.

CCI [REDACTED]

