### 5.2 Study Drug Administration

Based on the mechanism of action, PK/PD extrapolations, prior experience with lanadelumab in clinical trials, and supportive safety profile based on the existing clinical package, the recommended double-blind dose is an infusion of lanadelumab 300 mg or placebo IV, 1 dose on Day 1 and a second dose on Day 4.

The infusion of lanadelumab or placebo must be administered over a period of 60 minutes  $\pm$  15 minutes and must use an infusion set with an in line, sterile, non-pyrogenic, low protein-binding filter (pore size of 0.2  $\mu$ m or less). Infusion should begin within 3 hours of preparation. Refer to the Pharmacy Manual for a list of infusion sets and infusion pumps acceptable for use with lanadelumab.

The times of the beginning and the end of infusion will be recorded. Dosing interruptions will be recorded.

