14. EXPOSURE TO STUDY DRUG

Patients randomized to sub-protocol COV-01-001

Patients randomized to the Lanadelumab-IV + SoC or Placebo + SoC treatment groups of COV-01-001 sub-protocol will receive an IV injection of either Lanadelumab-IV 300 mg diluted in normal saline or placebo (normal saline), as applicable, in a double-blind manner, one dose on Day 1 and a second dose on Day 4, along with SoC.

Reason for dose modification of study drug (i.e., dose increased, dose reduced, drug interrupted and drug withdrawal) will be captured on the *Exposure* page of the eCRF.

Patients included in the control arm of COV-01-001 sub-protocol who were randomized to the Placebo + SoC group of a sub-protocol other than COV-01-001

It is to be noted that the planned duration of exposure to a study drug, planned frequency of administration of the study drug, and planned route of administration of the study drug will vary from one sub-protocol to the other, but similar information as for COV-01-001 sub-protocol will be captured on the *Exposure* page of the eCRF of these other sub-protocol.

Exposure to study drug

The exposure to study drug will be summarized by treatment arm (breaking down the Placebo + SoC arm by sub-protocol) based on the safety analysis set as follows:

- Duration of exposure:
 - Duration of exposure (days) as a continuous variable
 - Duration of exposure (days) as a categorical variable: 1 to 3, > 3 to 7, > 7 to 14, > 14 to 29, and > 29
 - Total number of doses received as a continuous variable, where the total number of doses received is defined as the total number of doses received by each patient, not the total number of doses received across all patients
 - For patients randomized to COV-01-001 sub-protocol only, number and percentages of patients who received only one dose and number and percentages of patients who received two doses.

- Dose modifications:
 - For patients randomized to COV-01-001 sub-protocol only, number and percentage of patients with at least one dose partially administered overall and for each dose
 - Number and percentage of patients with at least one interrupted dose
 - Number and percentage of patients with at least one dose interruption by reason for dose interruption:
 - Adverse events
 - Other.
 - Total number of dose interruptions as a continuous variable, where the total number of dose

CCI

[figure not shown]
PPD

Version Number: Amendment 3, v1.0
Version Date: 23-Jul-2021

CCI

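### Day 4 lanadelumab concentrations are summarized as one post-dose timepoint although the second infusion is given that day, so the summary may mix levels from before and after it

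*SAP*

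**What the plan says.** The regimen has two infusions. COV-01-001 SAP Section 14 gives it as "one dose on Day 1 and a second dose on Day 4, along with SoC", and sub-protocol Section 5.2 agrees: "1 dose on Day 1 and a second dose on Day 4".

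Only the Day 1 samples are tied to an infusion. For the later days, sub-protocol Section 4.2 makes sampling subject to feasibility and leaves the hour open: "plasma samples for PK analysis will also be collected on Days 4, 7, 15, and 29 (or hospital discharge, if earlier) at any time during". Footnote t of the Schedule of Activities says the same. Footnote d asks for the second infusion at about the clock time of the first.

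SAP Section 18 then treats the two dosing days differently. For the first: "For Day 1, PK concentrations of Lanadelumab-IV will be summarized for the pre- and post-infusion separately". For the second, Day 4 is placed with the non-dosing days: "Post-dose timepoints will be presented for Days 4, 7, 15, 29, and day of discharge as PK blood samples can be collected at any time". The listing follows the same scheme: "PK concentrations will be listed according to nominal time points scheduled".

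The information needed to do better is collected. Footnote t requires infusion start and end times for each dose, and adds: "All PK/PD sampling times (day, hour, minute) should be accurately recorded per 24-hour clock".

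**The concern.** The SAP justifies the single post-dose label by the fact that samples may be drawn at any hour. On Days 7, 15 and 29 no infusion is given, so the hour matters little for a drug whose half-life sub-protocol Section 2.0 puts at about 14 days. On Day 4 the free sampling time is exactly why a split is needed. The label is literally true of every Day 4 sample relative to the first dose, but it does not say whether the second had been given.

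If some patients are sampled before the second infusion and others after it, the Day 4 mean describes neither state and its CV partly measures draw time. After the end-of-infusion sample on Day 1, Day 4 is the only scheduled day that can inform the carry-over from the first dose or the rise after the second. The exposure it would describe is otherwise a model prediction from HAE data (sub-protocol Section 2.2). The SAP also plans to count patients who received only one dose (Section 14). For those patients a Day 4 sample follows dose 1 whatever the hour, and the current label would not show it.

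**Working it through.** **1. Reading the source table.** The inputs are in sub-protocol Table 1. The Cmax unit is printed as µg*mL and is read here as µg/mL. The stated margins were reproduced as monkey exposure divided by predicted human exposure.

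| Regimen | Measure | Calculation | Result | Stated |
|---|---|---|---|---|
| 300 mg | AUC | 123000/17281; 137500/17281 | 7.12; 7.96 | 7.1; 8.0 |
| 300 mg | Cmax | 1640/94.1; 1155/94.1 | 17.4; 12.3 | 17; 12 |
| 2×300 mg | AUC | 123000/33532; 137500/33532 | 3.67; 4.10 | 3.7; 4.1 |
| 2×300 mg | Cmax | 1640/130; 1155/130 | 12.6; 8.88 | 13; 8.9 |

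The table is internally consistent to rounding. The predicted Cmax values of 94.1 and 130 cannot themselves be rederived, because the model parameters are not given.

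**2. The widest gap that Day 4 could contain.** Assume linear superposition: the peak after dose 2 is the residue of dose 1 plus the peak of a single dose. The residue is then 130 − 94.1 = 35.9 µg/mL. The two extremes on Day 4 are about 36 µg/mL just before the infusion and 130 µg/mL at its end, a ratio of 130/35.9 = 3.6.

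**3. Effect on a pooled summary.** Let f be the share of Day 4 samples drawn after the infusion. The documents do not give f, so a range is shown. Put every sample at one of the two extremes: mean = 35.9 + 94.1f, and SD = 94.1·√(f(1 − f)).

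| f | Mean (µg/mL) | SD | CV from timing alone |
|---|---|---|---|
| 0.10 | 45.3 | 28.2 | 62% |
| 0.25 | 59.4 | 40.7 | 69% |
| 0.50 | 83.0 | 47.0 | 57% |
| 0.75 | 106.5 | 40.7 | 38% |
| 0.90 | 120.6 | 28.2 | 23% |

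**4. Why these are limits and not estimates.** A half-life of 14 days alone would bring 94.1 down to 94.1 × 2^(−3/14) = 81 µg/mL over three days. The superposed residue is 35.9. The predictions therefore imply a steep early fall, as expected from the two-compartment model named in Section 2.2. Samples taken hours after the second infusion may lie well below 130, and samples taken hours before it lie somewhat above 36. Both shrink the gap.

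**The case against.** The strongest reply is that little turns on this. Enrollment was terminated early and an abbreviated report is planned (SAP Section 3.3). Twenty-nine patients were randomized to the sub-protocol over both arms (Section 16), and the PK set takes the active arm only (Section 5.2). Master Protocol Section 8.6 says that PK is neither a primary nor a secondary objective. Minimum, median and maximum will be shown with the mean, individual concentrations and dosing data will be listed, and Master SAP Appendix 2 orders listings by date and time where applicable. A careful reader could partly reconstruct the split by hand. All of that stands. It limits the weight of the point, but it does not make the Day 4 row interpretable as planned.

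Three stronger readings are tempting, and the documents do not support them.

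- A reader might infer that pooling is what prevents a check of the predicted two-dose peak, and that splitting would restore it. It would not. Post-infusion draws on Day 4 are untimed, so their mean is not Cmax even after a split. That limit comes from the sampling scheme. End-of-infusion exposure is measured on Day 1, where it can be set against 94.1.
- A reader might infer that the safety margins depend on this peak. The tightest two-dose margins are those for AUC (3.7 and 4.1); those for Cmax are 13 and 8.9.
- A reader might extend the point to the day-of-discharge row and ask for bands of days since the last infusion. With so few patients, already broken down by baseline severity, the bands would leave very small cells.

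There are two further cautions. The SAP cites sub-protocol version 2.0 and the text available is version 1.2, but SAP Sections 14 and 18 establish the core alone. Footnote t and Section 4.2 also end in redactions, so other planned uses of the timed samples cannot be excluded.

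**Conclusion.** The point holds as a gap in the descriptive PK plan. The stated rule allows Day 4 samples from before and after the second infusion to be pooled under one label, while Day 1 is split. Mixing is permitted, not shown: it occurs only if samples fall on both sides of the infusion, and the documents do not say how many do.

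The size, 36 against 130 µg/mL, is an upper bound. It rests on linear superposition, on predictions fitted to HAE data, and on samples at the very start and end of the infusion. No efficacy or safety inference depends on it. In a PK set of fewer than 29 patients, however, a few samples on one side or the other could move the Day 4 mean noticeably.

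**What to change.** In SAP Section 18, compare each Day 4 sampling time with the recorded start of the second infusion. Summarize samples from before and after it separately, as is already done for Day 1. Where the second infusion was not given, class the sample as following dose 1 only. The heading of the later group should make clear that the draws are untimed, so that its mean is not read as a peak.

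The cost is a derivation and an extra table row. The sub-protocol already requires the infusion and sampling times to the minute; that this carries over to version 2.0 should be confirmed. The apremilast SAP (Section 18) already groups concentrations by time since dose, so the approach has a precedent within the trial.
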